IUGR	Intrauterine Growth Restriction
LFT	Liver Function Tests
LMP	Last Menstrual Period
MCA	Middle Cerebral Artery
MFM	Maternal Fetal Medicine
NEC	Necrotising Enterocolitis
NICU	Neonatal Intensive Care Unit
NO	Nitric Oxide
PI	Pulsatility Index
PPHN	Persistent Pulmonary Hypertension of The Newborn
PSV	Peak Systolic Velocity
RCT	Randomised Control Trial
REDF	Reversed Umbilical Arterial End Diastolic Flow
SAE	Serious Adverse Event
SAR	Serious Adverse Reaction
SGA	Small for Gestational Age
SMD	Subject Medication Diary
SUSAR	Suspected Unexpected Serious Adverse Reaction
UA	Umbilical Artery
UV	Umbilical Vein

1. SUMMARY

Severe early onset intrauterine growth restriction (IUGR) is associated with high rates of death before birth, death in the neonatal period and long term handicap as a consequence of being born so early and so small. We currently have no treatment for this disease other than close monitoring and (if the baby is mature enough and grown sufficiently to have a chance of survival) delivery when monitoring suggests the situation is 'in extremis'.

The majority of these cases are due to abnormal placental development and poor blood supply to the fetus. Sildenafil, as a vasodilator, has the potential to improve blood supply to the uteroplacental vessels and thus improve supply to the baby and possibly aid fetal growth. Data from a small case-control study suggest some potential benefits in fetal growth associated with sildenafil use in pregnancies with very early onset IUGR where the prognosis was otherwise extremely poor.

The purpose of this double blind randomised placebo controlled trial is to assess the effect of sildenafil on fetal growth in similar pregnancies with poor prognosis. The results will be combined with similar planned studies worldwide to assess its impact on the most important outcome of all, neonatal survival free of major handicap.

2. BACKGROUND

2.1 SGA and IUGR

Being born small for gestational age (SGA) is one of the three major complications of pregnancy and occurs in approximately 10% of pregnancies. Babies may be born SGA and with no complications (constitutionally small) or due to a failure to fulfil their full growth potential (IUGR). IUGR may occur for a number of reasons including abnormal fetal karyotype, fetal syndrome or anomaly and fetal infection. However the majority of cases of fetal growth restriction are due to abnormal placentation and are part of a spectrum of placental ischaemic conditions including preeclampsia and abruption.

IUGR occurring early in pregnancy is rare, affecting 0.2% of pregnancies <28 weeks gestation. Due to the severity of disease and extreme prematurity the risks to the fetus and infant are very high. Babies may die in-utero before reaching viable gestations or weights and are susceptible to the effects of hypoxia which may result in poor health in the neonatal period, as children and through to adulthood. There is currently no therapy to improve outcome once growth restriction has occurred and therefore the only treatment clinicians are able to offer is timely delivery. Intense monitoring aims to predict when the fetus has maximised its time in-utero and the risk of hypoxia and death is so high that early delivery is indicated. However, this often results in extreme preterm birth and its inherent risks including death, severe neonatal morbidity and again potential life-long health consequences. Recent North American data suggests of

infants delivered at 24-28 weeks with birthweight <10th centile, only 25% survive free of major morbidity, however by 30-32 weeks more than three quarters (78%) survive free of major morbidity [1].

Along with very significant health risks for these IUGR preterm babies there is an enormous emotional and financial burden for individuals, families, health care providers and society. The direct costs of their care, including the increased cost of intensive antenatal surveillance (and likely period of hospitalization), Caesarean delivery, neonatal intensive care, paediatric follow-up including specialised neurodevelopmental assessments and interventions, as well as the indirect costs to families (lost wages, supportive services, and relationship stress), contribute to a vastly disproportionate level of investment in these pregnancies. Therapy allowing expectant management and safe pregnancy prolongation could be associated with significant societal and financial savings.

2.2 Pathophysiology

The process of human placentation is central to reproductive success but complex and poorly understood. In normal pregnancy the uteroplacental circuit undergoes significant changes with extravillous trophoblast remodelling the maternal spiral arteries converting a high resistance, low flow circulation to a low resistance, high flow circulation, resulting in efficient gaseous and nutrient exchange across the placenta. In the process of normal spiral artery remodelling there is 'boring out' of the smooth muscle of these medium sized resistance vessels with removal of the nitric oxide (NO)-producing endothelium, the internal elastic lamina and the NO-responsive muscularis layers. The resulting effect of this removal of these layers by extravillous trophoblast is a system of vessels unresponsive to normal regional vascular control. Blood flow becomes predominantly modulated by changes in mean arterial pressure and regional blood flow diversion (e.g. to the thighs and buttocks during exercise).

IUGR (and preeclampsia) occurs as a consequence of inadequate or abnormal placental invasion and spiral artery remodelling leading to abnormalities of the maternal and/or fetal vascular compartments. This is reflected in abnormal Doppler waveforms of both fetal and maternal uteroplacental vessels. In IUGR poor gaseous and nutrient exchange across the placenta occurs as a result leading to poor growth and ultimately hypoxia and death. In preeclampsia the abnormal placenta results in release of vasoactive substances into the maternal circulation and the clinical scenario of this hypertensive disease.

2.3 Potential of sildenafil, a NO-donor

Incomplete remodelling of maternal spiral arteries in cases of abnormal placentation results in a uteroplacental circulation with high resistance and low flow. The vessels have intact or partially intact muscular layers and so potentially remain responsive to nitric oxide. Sildenafil is a nitric oxide donor causing vasodilatation and so has the

potential to increase uteroplacental circulation and perfusion thus improving gaseous and nutrient exchange and fetal growth.

Animal Studies

In a mouse model of IUGR (catechol-O-methyl transferase knockout mouse (COMT-/-)) measures of pup growth, including body weight, crown/rump length and abdominal circumference were reduced compared to control mice. Treatment with sildenafil from gestational day 12.5 to 18.5 demonstrated normalisation of all growth measures. Despite no significant increase in uterine artery flow measured by Doppler waveform studies, abnormal umbilical Doppler waveforms (including reversed arterial blood flow velocity) normalized following treatment with sildenafil – suggesting a beneficial effect on fetoplacental blood flow [2]. Increased growth parameters have also been demonstrated in rat and guinea pig models [3, 4].

Human studies

In humans, ex vivo myometrial small artery function is aberrant in IUGR and sildenafil appears to improve vasodilatation in IUGR pregnancies. This has been demonstrated using small arteries dissected from myometrial biopsies obtained at Caesarean section from 27 normal pregnant women and 12 women whose pregnancies were complicated by IUGR [5]. Arteries were mounted on wire myographs and vessels constricted (with arginine vasopressin or U46619) and relaxed (with bradykinin) before and after incubation with sildenafil. Sildenafil significantly reduced vasoconstriction and significantly improved relaxation of IUGR small arteries.

2.4 Sildenafil in Pregnancy

As a nitric oxide donor, sildenafil is used in the management of pulmonary arterial hypertension for vasodilatation of pulmonary vasculature. There are now many case reports of its use in pregnancy [6-8] with improved maternal cardiorespiratory performance and echocardiographic status and delivery of healthy infants.

It is also increasingly used in the neonatal period in infants (including those born preterm) for the treatment of persistent pulmonary hypertension of the newborn (PPHN). PPHN occurs as a result of failure of the pulmonary vasculature to relax at birth and consequent lack of the normal neonatal cardiorespiratory adaptation leading to hypoxaemia. This condition is more common in preterm infants and the risk of mortality and morbidity is high. Sildenafil selectively reduces pulmonary vascular resistance and appears to be a useful adjunctive therapy to current care including inhaled nitric oxide (iNO) therapy, surfactant and high-frequency oscillatory ventilation [9].

Interest in the use of sildenafil for the treatment of other placental ischaemic conditions has led to a small placebo controlled randomised trial of its use in women with early onset preeclampsia (NCT 00141310) [10]. In this British study, 35 women with preeclampsia at gestational ages 24–34 weeks were recruited from nine hospitals and

randomly assigned to sildenafil or placebo at gradually increasing daily doses. The primary endpoint was prolongation of pregnancy from randomisation to delivery. Details of all adverse events were collected. There was no difference in time from randomisation to delivery in the two treatment groups, with a median time of 4 days (range 1–15) in the sildenafil group and 4.5 days (range 1–30) in the placebo group. The median birthweights in the sildenafil and placebo treated groups were 1410g (range 553-2480) and 1043g (range 519-2510g) respectively, $p>0.1$. At all doses, Sildenafil was well tolerated with no increase in maternal or fetal morbidity or mortality.

Plasma samples were taken to establish pharmacokinetic information. Sildenafil achieved maximum drug concentrations of 48ng/ml, 88ng/ml, and 271ng/ml after 3 days of 20mg, 40mg and 80mg tds respectively.

2.5 Sildenafil and IUGR – Clinical experience

[figure not shown]
Whilst working in Canada, [name] has gained, and published his, experience of the use of sildenafil in women with severely growth restricted fetuses [11]. Within the British Columbia Provincial Health Services Authority there is a process for offering patients innovative therapy through formal information sharing and consenting process. Through this mechanism, patients facing dire prognoses can be offered innovative therapeutic interventions. Under this rubric, sildenafil treatment was included in the management of a series of 10 women with severe early onset IUGR and, for analytical purposes, their outcomes were compared with a series of 17 women who fulfilled the treatment criteria but either declined or were not offered Sildenafil. The demographics and outcomes are summarised in Table 1.

The women who received sildenafil treatment tended to have poorer indices of fetal well-being at baseline in terms of umbilical artery Doppler flow waveforms and amniotic fluid indices. Other than one woman who suffered a stillbirth within 48h of commencing sildenafil treatment, all sildenafil treated fetuses had increased fetal abdominal circumference growth velocity after treatment (odds ratio 12.9 [95% CI 1.3 - 126] Figure 1). Sildenafil treated fetuses tended to be more frequently live born and to survive intact to primary hospital discharge.

Table 1: Demographic & outcome data case-control study of sildenafil for severe early onset IUGR [11]. Expressed as median [interquartile range] or absolute number (%).

	Sildenafil-naïve (n=17)	Sildenafil-treated (n=10)	p value
Demographics			
Maternal age at EDD (years)	33 [28, 36.5]	34 [25, 40.5]	0.73
Nulliparous	8 (47%)	5 (50%)	1.00
GA at eligibility (days since LMP)	148 [137.5, 163]	158 [147.5, 164.5]	0.15
Uterine artery notching at eligibility	10 (59%)	8 (80%)	0.41
AC <1 st percentile at eligibility	10 (59%)	6 (60%)	1.00
Umbilical artery Doppler positive EDF	13 (76%)	5 (50%)	0.22
Amniotic fluid index >50mm	15 (88%)	6 (60%)	0.15
Outcomes			
Secondary development of preeclampsia	5/9 (56%)	2/12 (17%)	0.16
Fetus with increased AC growth velocity post-eligibility/on Sildenafil	7 (41%)	9 (90%)	0.02
Eligibility-to-delivery interval (days)	42 [17, 55]	31.5 [9.5, 81]	0.87
GA at delivery (days since LMP)	180.5 [165.5, 208]	189.5 [178.5, 229.5]	0.28
Live birth	6 (35%)	7 (70%)	0.12
Survival	6 (35%)	5 (50%)	0.69
Intact survival	5 (29%)	5 (50%)	0.42

Figure 1: Change in daily AC growth pre versus post-eligibility epochs.[11]

As yet there is no treatment for severe early onset IUGR other than delivery of the fetus with the inherent risks of extreme prematurity. This improvement in fetal growth after sildenafil treatment is exciting and if confirmed has potential for future therapy in these very high risk pregnancies. However, a great deal more evidence, both in terms of safety and outcome data, is required before it can be used in clinical practice.

STRIDER NZAus is a double blind randomised placebo controlled trial. It is designed with sufficient power to assess the effect of sildenafil on fetal growth velocity and further explore its safety profile in pregnancies complicated by severe early onset IUGR. STRIDER NZAus will be led by investigators at the University of Auckland and will recruit women from Maternal Fetal Medicine (MFM) centres across New Zealand and Australia.

The STRIDER IPD Collaboration is an international collaboration of individual patient data (IPD) analysis of several national (and bi-national) STRIDER RCTs. This prospectively planned IPD will have sufficient power to assess the effect of sildenafil on rates of survival without major morbidity in pregnancies complicated by severe early onset IUGR. Other STRIDER trials are planned in Ireland, Canada, United Kingdom and the Netherlands. The STRIDER IPD Collaboration will be led by [name] [name], University of British Columbia, Canada and [name], University of Auckland, New Zealand.

3. TRIAL HYPOTHESIS & AIMS

3.1 Hypothesis

The primary hypothesis is: sildenafil therapy compared to placebo therapy will increase the likelihood of increased fetal growth velocity (measured by change in expected/observed increase in abdominal circumference per day) in pregnancies complicated by severe early onset IUGR.

This hypothesis has been set in line with the STRIDER IPD Collaboration.

3.2 Primary Aim

To assess the effect of sildenafil compared to placebo therapy on the proportion of pregnancies that have an increase in fetal growth velocity (measured by change in expected/observed increase in abdominal circumference per day) in pregnancies complicated by severe early onset IUGR.

This aim has been selected in line with the STRIDER IPD Collaboration.

3.3 Secondary Aims

Effects on fetal growth and well-being:

1. To compare mean absolute change in abdominal circumference (mm) per day in fetuses treated with sildenafil and placebo.
2. To compare measures of uteroplacental, umbilical and fetal Doppler waveform studies in those treated with sildenafil and placebo.
3. To compare customised birthweight centiles in infants treated in-utero with sildenafil and placebo.

Effects on outcome:

1. To compare live-birth rates of infants treated in-utero with sildenafil and placebo.
2. To compare survival without major morbidity rates to EDD or hospital discharge (whichever comes later) of infants treated in-utero with sildenafil and placebo.

To report frequency of adverse and serious adverse events associated with sildenafil use.

Myometrial and placental myography studies (Auckland Study Centre only):

1. To compare the effect of sildenafil and placebo on vascular endothelial and vascular smooth muscle cells in myometrium.
2. To compare the effect of sildenafil and placebo on chorionic plate and stem villous blood vessels within the placenta.

3.4 Aim of STRIDER IPD Collaboration

To assess the effect of sildenafil compared to placebo therapy on the rates of infant survival without major morbidity (no evidence of CNS injury, bronchopulmonary dysplasia requiring home oxygen therapy, \geq grade 3 ROP or NEC) in pregnancies complicated by severe early onset IUGR. Outcome data relating to this outcome will be collected in STRIDER NZAus.

4. TRIAL & DRUG SAFETY

4.1 Potential Risks of IUGR to the Baby

There are significant risks for a fetus with severe early onset growth restriction. In-utero death may occur prior to reaching a viable gestational age or birthweight and, of infants born alive, 30% will die in the neonatal period and only 25% survive free of major morbidity [1].

4.2 Potential Risks of IUGR to the Mother

The main risk to the mother with severe early onset IUGR pregnancy is the development of secondary pre-eclampsia. 40% of cases of early onset IUGR are likely to develop co-existing preeclampsia. Close and systematic maternal assessment and surveillance is essential to monitor for preeclampsia. In addition if the fetus is considered viable and

delivery is required for severe early onset IUGR, operative caesarean section is almost always required to safely deliver the 'at risk' infant.

4.3 Potential Risks of Sildenafil Treatment

The most common sildenafil related side effects are headache, flushing, dyspepsia, nasal congestion and impaired vision, including photophobia and blurred vision. (Sildenafil Citrate Data Sheet. Actavis. www.medsafe.govt.nz/profs/datasheet/s/silagratab.pdf). None of the women treated with sildenafil for severe early onset IUGR at British Columbia Women's Hospital complained of side effects [11] and sildenafil was similarly well tolerated in the UK RCT for pre-eclampsia [10]. Women will be asked to verbally report side effects and record these in their Subject Medication Diary (SMD) and this data will be collected in the CRF.

It is possible that sildenafil may improve fetal growth velocity to gain gestational age and maturity to a level that an infant that would have demised in-utero actually survives but due to the nature of extreme preterm birth and growth restriction has significant long term handicap. However if sildenafil does demonstrate an improvement in fetal growth velocity that results in improved survival, it is likely that it will also improve fetal growth in babies that would usually have survived with handicap to allow them to reach an age and size where handicap is less likely. One of the primary aims of this study is to assess this potential impact.

It is also possible that sildenafil has no effect or a negative effect on fetal growth velocity. In addition, vasodilatation in an already compromised fetus (with abnormal fetal Doppler waveforms) may lead to decompensation and earlier demise of a sick fetus. These possibilities can only be accurately assessed through an RCT of this nature.

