SAEs must also be assessed for expectedness in this clinical setting. The Investigator is responsible for determining whether an SAE is expected or not based on the underlying severe IUGR and the published reference safety information for sildenafil (this can include a sildenafil Investigator's Brochure, MedSafe/TGA product Data Sheets and this protocol). An unexpected adverse event/reaction is one that is not reported in the reference safety information, is more severe than previously reported or is not reasonably explained by the underlying condition.

Review of all of the known information about the SAE should conclude one of the following:

Expected Events:

- Expected Unrelated Event: the SAE is expected based on the known information about the study drug or the underlying condition and is not considered to be related to the study drug. This is referred to as an Expected SAE.
- Expected Related Event: an SAE which the Investigator considers possibly, probably or definitely related to the study drug. This is referred to as a SAR – Serious Adverse Reaction.

Unexpected Events:

- Unexpected Unrelated Event: the SAE is unexpected based on the known information about the drug or the underlying condition and is not considered related to the study drug. This is referred to as an Unexpected SAE.
- Unexpected Related Event: the SAE is unexpected based on the known information about the drug or the underlying condition and is considered possibly, probably or definitely related to the study drug. This is referred to as a SUSAR – Suspected Unexpected Serious Adverse Reaction.

In this cohort of early-onset severe IUGR and with the lack of an alternative therapy, fetal or neonatal death due to complications of severe IUGR or prematurity and prolonged stay in the neonatal unit and may occur and in this setting and so may be Expected Events (Expected SAEs). These fetal or neonatal deaths in the study reporting period will be recorded as SAEs on the CRF but do not require immediate reporting unless the Investigator has specific concerns about these events or believes they are likely to be causally related to the study drug i.e. considered as a SAR or SUSAR.

Maternal death and maternal life-threatening complications should always be considered unexpected events in this population and require immediate reporting.

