16.2 Secondary outcomes

Secondary outcomes include:

- Additional measures of fetal growth and wellbeing: mean absolute change in abdominal circumference (mm) per day, mean birthweight and mean birthweight centile, amniotic fluid index, deepest vertical amniotic fluid pocket and short term variability (STV) measured by computerised cardiotocography (CTG).
- Changes in uteroplacental, umbilical and fetal Doppler waveform studies.
- Maternal symptomatic hypotension, headaches, flushing and pre-eclampsia
- Randomisation-to-delivery interval, gestational age at delivery, mode of delivery and postpartum haemorrhage requiring transfusion.
- Measures of neonatal outcome; rates of intrauterine death, live-births, survival to hospital discharge, major morbidity including chronic lung disease requiring ambulatory oxygen therapy on hospital discharge, intraventricular haemorrhage grade 3-4, \geq grade 3 retinopathy of prematurity, necrotising enterocolitis, number of doses of surfactant, ventilator days, supplemental oxygen days and number of days to full feeds.
- Any adverse or serious adverse events.

For Auckland Study Centre

The effect of sildenafil compared to placebo will be assessed by vascular physiological studies:

- Of myometrial vascular endothelial and vascular smooth muscle cells
- Of placental chorionic plate and stem villous blood vessels.

16.3 Primary outcome of STRIDER IPD Collaboration.

The rate of infant survival without major morbidity (no evidence of CNS injury, bronchopulmonary dysplasia requiring home oxygen therapy, \geq grade 3 ROP or NEC).

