17. STATISTICAL ANALYSES

Data will be analysed on an intention-to-treat basis.

Demographic and other baseline data will be summarised by study treatment groups. For continuous outcomes, t-test, linear regression and mixed model for repeated measures method will be used where appropriate. For categorical outcomes, Fisher's exact test, logistic regression and generalised linear mixed effects model will be used where appropriate. Two sided-p-values less than 0.05 will be used to determine statistical significance and all confidence intervals will be reported at a two sided 95% level.

Details of statistical analysis method are described in the Statistical Analysis Plan.

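### Earlier fetal death is named as a possible harm, but fetal death is an outcome only as an overall rate, which responds weakly to early drug-related deaths

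*Protocol*

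**What the plan says.** Protocol section 4.3 raises the possibility that vasodilatation in an already compromised fetus "may lead to decompensation and earlier demise of a sick fetus", and adds: "These possibilities can only be accurately assessed through an RCT of this nature".

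The places where fetal death or its timing could be picked up are these:

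- Section 16.2 lists "rates of intrauterine death, live-births, survival to hospital discharge", with no time point and no time-to-death or gestation-at-death outcome.
- Section 3.3 has the matching aim: "To compare live-birth rates of infants treated in-utero with sildenafil and placebo". Its safety aim is to report how often adverse and serious adverse events occur.
- Section 16.2 also lists "Randomisation-to-delivery interval, gestational age at delivery, mode of delivery". These carry timing but pool live and dead births.
- Section 13.2 makes fetal death a serious adverse event. Section 13.3 requires start and stop dates for each event and says of expected deaths: "These fetal or neonatal deaths in the study reporting period will be recorded as SAEs on the CRF".
- Section 17 names methods for continuous and categorical outcomes ("For continuous outcomes, t-test, linear regression and mixed model for repeated measures method will be used where appropriate"; Fisher's exact test and logistic models for categorical ones) and leaves the detail to the SAP, which is not at hand.

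**The concern.** The harm in section 4.3 is one of timing: a sick fetus dies sooner than it otherwise would. The outcome that names fetal death records only whether death occurred. In a population where many fetuses die before birth, early drug-related deaths are diluted in the overall rate. If they fall on fetuses that would have died in utero later, they leave no trace in it. If the drug also prevents some later deaths, the overall rate could even look favourable while early deaths have increased.

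At stake is how the trial's safety result is read. Similar overall fetal-death rates could be taken as reassurance about section 4.3, although the comparison has little ability to provide it.

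**Working it through.** The protocol gives no figure on this point to reproduce. Only the sample size enters: the continuity-corrected two-proportion formula for 50% v 80% gives the stated 58 per group, and 116 × 1.05 = 121.8, so 122 in total or 61 per arm.

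**Assumed inputs.** The protocol gives no rate of intrauterine death and no death times. The nearest guide is the series in section 2.5, Table 1, with live birth in 6/17 untreated and 7/10 treated women, so 11/17 (65%) and 3/10 without a live birth. I therefore vary background fetal death p from 20% to 65%. Background death times are taken as exponential with mean 30 days, so the share of deaths falling by day 7 is F = 1 − exp(−7/30) = 0.208. Tests are Fisher's exact, two-sided 0.05. Powers in steps 1 and 2 were obtained by enumerating the two binomial distributions.

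**1. Early drug deaths independent of later fate.** A fraction e of treated fetuses dies in week 1 regardless of what would have followed.

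- Overall rate: p v e + (1 − e)p
- By day 7: pF v e + (1 − e)pF
- Example, p = 0.30 and e = 0.20. Overall: 0.30 v 0.20 + 0.80 × 0.30 = 0.44. By day 7: 0.062 v 0.20 + 0.80 × 0.062 = 0.250.

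| p | e | Overall rates | Power | Day-7 rates | Power |
|---|---|---|---|---|---|
| 30% | 20% | 30% v 44% | 0.29 | 6% v 25% | 0.78 |
| 50% | 20% | 50% v 60% | 0.16 | 10% v 28% | 0.64 |
| 65% | 20% | 65% v 72% | 0.09 | 14% v 31% | 0.56 |
| 30% | 10% | 30% v 37% | 0.09 | 6% v 16% | 0.27 |

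The overall rate moves in the right direction, but by less as background loss rises.

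**2. Deaths only brought forward.** The same share p dies in both arms, and a fraction q = 0.40 of treated deaths moves into week 1.

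- Overall rates are equal by construction, so rejection at about 3% is the size of the test and not a finding.
- By day 7: pF v p[q + (1 − q)F]. For p = 0.30: 0.062 v 0.30 × (0.40 + 0.60 × 0.208) = 0.157.
- Power of the day-7 comparison: 0.71 at p = 65%, 0.54 at 50%, 0.28 at 30%, 0.15 at 20%.

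**3. Hastened death pre-empts live delivery.** Take constant hazards, with the death hazard multiplied by HR and the live-delivery hazard unchanged. The overall rate becomes HR·p/(HR·p + 1 − p). For p = 0.30 and HR = 2 this is 0.60/1.30 = 46%. Power is about 0.45 by the normal approximation and 0.38 with Fisher's test. With HR = 3 the normal approximation gives 0.72 to 0.84 for p between 20% and 65%. Here the overall rate does respond.

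**4. Interval from randomisation to delivery, as listed** (simulated; live-delivery times also assumed).

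- In the setting of step 2 its power is 0.46, 0.28 and 0.13 at p = 65%, 50% and 30%. The day-7 comparison in the same runs has about 0.70, 0.54 and 0.29.
- If the median time to death is instead halved from 14 to 7 days, the interval has 0.11 (p = 30%) and 0.28 (p = 50%), and day-7 deaths 0.11 and 0.22.

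So day-7 counts are not always the more powerful. Their advantage is that they separate fetal death from early live delivery, which the interval cannot do.

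**The case against.** A reader might infer more than the documents support.

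- **That the overall rate cannot show the harm.** It can. Surviving fetuses are delivered, so a death that comes before a live delivery adds to the rate (step 3). It is blind only to deaths that would have happened in utero anyway, or that are offset by later deaths prevented.
- **That the protocol promises a test and omits it.** Section 4.3 justifies randomisation. It implies that the trial will inform the question but states no hypothesis about time to death.
- **That timing and early deaths are ignored.** Delivery interval and gestation at delivery are listed, fetal deaths are dated serious adverse events, those judged drug-related are reported immediately, and data safety monitoring boards exist. These routes are real but indirect: the first two mix live and dead births, and the safety aim is frequency.
- **That the earlier series shows hidden harm.** It reports "Other than one woman who suffered a stillbirth within 48h of commencing sildenafil treatment". That is one event, in a treated group with poorer baseline indices, and no death times are given for the untreated women.
- **That 65% fetal death applies here.** The untreated women's median gestation at eligibility was 148 days, below the trial's minimum of 22 weeks (22 × 7 = 154 days). Table 1 also reports live birth, not intrauterine death. Lower rates are plausible, and the added analysis has less power there.

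The strongest objection is that the SAP may present fetal death by time. That holds for the method, and section 17's silence on time-to-event methods is no fault. The outcome itself, however, is fixed in section 16.2 as a rate.

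**Conclusion.** The point holds in limited form. Section 4.3 names earlier death of a compromised fetus as a possible harm, and no outcome in section 16.2 compares the timing of fetal death between arms. The overall rate is insensitive to early drug-related deaths when background loss is high and blind to those that would have occurred in utero in any case. The other timing information does not separate fetal death from live delivery.

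With 61 per arm, 30% background death and 20% early drug deaths, power is about 0.29 for the overall rate and 0.78 for deaths by day 7. If 40% of deaths are only moved into week 1, the day-7 comparison has about 0.28 at 30% fetal death and about 0.15 at 20%. Death rates, death times and effect sizes are all assumptions, so these figures show direction and rough size only. This is a cheap improvement to the safety reporting; the primary analysis is not affected.

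**What to change.** Keep the overall rate of intrauterine death. Add to section 16.2, as a secondary safety outcome, the cumulative incidence of intrauterine death from randomisation by arm, in all randomised women, with live delivery as a competing event. Report counts by arm at 48 hours, 7 days and 14 days, with confidence intervals for the differences. Present it as an estimate and not as the test of a stated hypothesis, and say that a lack of difference is weak reassurance if fetal deaths are few.

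Cost: one more secondary comparison and one competing-risk analysis. The dates of randomisation, delivery and fetal death are already collected under the protocol, so no extra women, visits or data items are needed.
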